8.6 Sample Size Calculation

An equivalence test of means using two one-sided tests on data from a parallel-group design with sample sizes of 266 in the SPIL's Brinzolamide ophthalmic suspension 1% and 266 in Azopt® 1% achieves 90% power at an $\alpha = 0.05$ significance level when the true difference between the means is 0, the standard deviation is 3.5, and the 95% equivalence limits are -1.0 and 1.0.

Considering the possibility of 20% of subjects not being evaluable either due to dropping out of the study or having major protocol violations, approximately 333 subjects will be enrolled in each treatment group for a total of 666 subjects in the study.

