### **Sample size and statistical approach to primary analysis**

An equivalence test of means using 2 one-sided tests on data from a parallel-group design with sample sizes of 266 in the SPIL's Brinzolamide ophthalmic suspension 1% and 266 in Azopt® 1% achieves 90% power at an  $\alpha = 0.05$  significance level when the true difference between the means is 0, the standard deviation is 3.5, and the 95% equivalence limits are -1.0 and 1.0. Considering the possibility of 20% of subjects not being evaluable either due to dropping out of the study or having major protocol violations, approximately 333 subjects will be enrolled in each treatment group for a total of 666 subjects in the study.

**Efficacy analyses:** The primary analyses will be completed by constructing two-sided 95% confidence intervals of the treatment difference (test – reference) for mean IOP of both eyes (continuous variable) at all 4 follow-up points i.e., at approximately 8:00 AM. (hour 0; before the morning drop) and 10:00 AM. (hour 2) at the Day 14 (Week 2) and Day 42 (Week 6) visits. This mean IOP must be within  $\pm 1.5$  mm Hg using the per protocol (PP) population for all time points measured and within  $\pm 1.0$  mm Hg using the PP population for the majority of time points measured.

**Safety analyses:** The primary safety analysis will summarize ocular (in both eyes) and non-ocular AEs for all treated subjects using discrete summaries at the subject level by Medical Dictionary for Regulatory Activities (MedDRA®) system organ class (SOC) and preferred term (PT) for each treatment group. A treatment emergent adverse event (TEAE) will be defined as occurring after the first dose of study medication for the period. Treatment-related ocular and non-ocular TEAEs will be summarized similarly. Ocular and non-ocular TEAEs will also be summarized by severity.

| [Redacted] | [Redacted] | [Redacted] | [Redacted] | [Redacted] | [Redacted] |
|------------|------------|------------|------------|------------|------------|
| [Redacted] | [Redacted] | [Redacted] | [Redacted] | [Redacted] | [Redacted] |
| [Redacted] | [Redacted] | [Redacted] | [Redacted] | [Redacted] | [Redacted] |
| [Redacted] | [Redacted] | [Redacted] | [Redacted] | [Redacted] | [Redacted] |
| [Redacted] | [Redacted] | [Redacted] | [Redacted] | [Redacted] | [Redacted] |
| [Redacted] | [Redacted] | [Redacted] | [Redacted] | [Redacted] | [Redacted] |

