## **10.3 Efficacy Analysis**

The accepted PP population used for BE evaluation includes all randomized subjects who meet all inclusion/exclusion criteria, instill a pre-specified proportion of the scheduled doses (i.e., compliance between 75 to 125%) of the assigned product for the specified duration of the study,

and complete evaluations at Day 14 (Week 2) and Day 42 (Week 6) with no protocol violations that would affect the treatment evaluation.

Subjects whose condition worsens (e.g., IOP  $\geq$  36 mm Hg in either eye) and require alternate or supplemental therapy for the treatment of their chronic open angle glaucoma or ocular hypertension during the study should be discontinued, excluded from the PP population analysis, and provided with effective treatment.

Analysis will be done in both eyes. The primary analyses will be completed by constructing two-sided 95% confidence intervals of the treatment difference (test – reference) for mean IOP of both eyes (continuous variable) at all four follow-up points (i.e., at approximately 8:00 a.m. [hour 0; before the morning drop] and 10:00 a.m. [hour 2] at the Day 14 [Week 2] and Day 42 [Week 6]) visits. This mean IOP must be within  $\pm$  1.5 mm Hg using the PP population for all time points measured and within  $\pm$  1.0 mm Hg using the PP population for the majority of time points measured. Additional details of the statistical approach considering country wise analysis will be provided in the SAP.

For change from baseline IOP, baseline will refer to the time-matched measure at Visit 2. For all other variables, baseline is defined as the last measurement prior to the first dose of study medication. Change from baseline will be calculated as visit – baseline. The p-values for testing equivalence of these time-matched means between treatment groups will be generated using the TOST (two one-sided tests) procedure at each of the equivalence limits (-1.0, 1.0) and (-1.5, 1.5).

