## **10.5 Sample Size**

An equivalence test of means using two one-sided tests on data from a parallel-group design with sample sizes of 266 in the SPIL's Brinzolamide ophthalmic suspension 1% and 266 in Azopt® 1% achieves 90% power at an  $\alpha = 0.05$  significance level when the true difference between the means is 0, the standard deviation is 3.5, and the 95% equivalence limits are -1.0 and 1.0.

Considering the possibility of 20% of subjects not being evaluable either due to dropping out of the study or having major protocol violations, approximately 333 subjects will be enrolled in each treatment group for a total of 666 subjects in the study.

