9.6.1 Primary Efficacy Endpoint

Mean difference in IOP of both eyes between the two treatment groups at four time points, i.e., at approximately 8:00 a m. (hour 0; before the morning drop) and 10:00 a.m. (2 hours) at the Day 14 (Week 2) and Day 42 (Week 6) visits

IOP measurements will be taken using a Goldmann applanation tonometer. IOP will be measured at least twice in each eye with the right eye measured first. If the difference of the first 2 measurements is ≤ 1 mm Hg, the average of these 2 measurements will be used as the IOP data for this eye. If the difference is > 1 mm Hg, a third measurement will be taken, and the median of these 3 measurements will be used as the IOP data for this eye.

Two-sample 95% CIs around the difference in the mean IOP (both eyes) at each timepoints i.e., at approximately 8:00 a m. [hour 0; before the morning drop] and 10:00 a.m. [hour 2] at the Day 14 [Week 2] and Day 42 [Week 6]) visits will be constructed using a two-sample t-distribution.

The hypotheses for a two-sample equivalence test are:

 H_o : $\mu < \Theta_L$ or $\mu > \Theta_U$

[figure not shown]
 $H_1: \Theta_L \le \mu \ge \Theta_U$

Where.

μ: Difference in mean IOP between treatment groups within study period

 $\Theta_{L:}$ -1.5mm Hg and (-1.0mm Hg)

 $\Theta_{U:}$ 1.5mm Hg and (1.0mm Hg)

The overall p-value of the equivalence test will be reported, which is the larger of the two p-values of the tests L and U. Rejection of H_0 in favour of H_1 at significance level α occurs if and only if the 100 (1-2 α) % confidence interval for μ is contained within (-1.5, 1.5) and (-1.0, 1.0). Two sample t-test also assumes equality of variances in the treatment groups, hence depending on the results from Levene's test, CI, and p-values from Equal (Pooled) or Unequal (Satterthwaite) variance will be reported.

This analysis also will be tested for ITT population to check the robustness of the result.

[figure not shown]

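### The stated 90% power belongs to a 90% confidence interval, but the primary analysis uses 95% intervals (about 82% power per time point), and SAP 9.6.1 and 9.6.2 give no α for the rule that decides equivalence

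*SAP*

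**What the plan says.** **Sizing.** The synopsis, protocol 10.5 and SAP 8.6 carry the same calculation. SAP 8.6 describes "An equivalence test of means using two one-sided tests on data from a parallel-group design", with 266 evaluable subjects per arm, which "achieves 90% power at an $\alpha = 0.05$ significance level when the true difference between the means is 0, the standard deviation is 3.5". Protocol 10.5 completes the assumptions: "the standard deviation is 3.5, and the 95% equivalence limits are -1.0 and 1.0". An allowance of 20% non-evaluable subjects takes 266 to 333 per arm, 666 in total.

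**Primary analysis.** The synopsis and protocol 10.3 both state: "The primary analyses will be completed by constructing two-sided 95% confidence intervals of the treatment difference". The success rule follows directly: within ±1.5 mm Hg at all four time points and within ±1.0 mm Hg at the majority of them, in the per protocol population. SAP 9.6.1 also builds "Two-sample 95% CIs around the difference in the mean IOP (both eyes) at each timepoints".

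**Decision rule.** SAP 9.6.1 then says that rejection at significance level α "occurs if and only if the 100 (1-2 α) % confidence interval for μ is contained within" the limits. SAP 9.6.2 repeats this for change from baseline. Neither section gives α a number. Protocol 10.3 adds: "The p-values for testing equivalence of these time-matched means between treatment groups will be generated using the TOST" procedure, at both pairs of limits, again without an α.

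**The concern.** Two one-sided tests at level α per side correspond to a 100(1-2α)% interval. A test at 0.05 per side therefore goes with a 90% interval, and a 95% interval goes with 0.025 per side. The sizing sections name 0.05, the analysis sections name 95%, and the SAP's formal rule names neither.

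Two things follow. First, if the 95% intervals decide, the stated 90% is not the power of the planned analysis. Second, if the only α in the documents is put into the SAP's own formula, the deciding interval is 90%, which contradicts the 95% interval built earlier in the same section. The two levels can give opposite verdicts on the same data, so a confirmatory pass/fail rule should not leave room for either. The type I error is not inflated under either reading. The 95% interval is the stricter one.

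**Working it through.** **Inputs** (SAP 8.6 and protocol 10.5): n = 266 evaluable per arm, SD 3.5 mm Hg, true difference 0, limits ±1.0 mm Hg.

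**Formula.** Standard error SE = 3.5 × √(2/266) = 0.3035. With a true difference of 0, the normal approximation to the power of two one-sided tests at level a per side is 2Φ(1.0/SE − z(1−a)) − 1, and 1.0/SE = 3.295. The exact version uses the t critical value on 530 degrees of freedom and integrates over the chi-square distribution of the pooled variance.

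**Step 1: reproduce the plan's figure (0.05 per side, 90% interval).**
- Normal: 2Φ(3.295 − 1.645) − 1 = 2 × 0.9505 − 1 = 90.1%.
- Exact: 90.0%. The smallest n that reaches 90% is exactly 266 per arm.
- 266/0.8 = 332.5, rounded up to 333 per arm, 666 in total.

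All the stated numbers reproduce, and they show that the sizing used 0.05 per side.

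**Step 2: same n with the 95% interval (0.025 per side).**
- Normal: 2Φ(3.295 − 1.960) − 1 = 2 × 0.9091 − 1 = 81.8%.
- Exact: 81.6%. The chance of missing equivalence at one time point rises from 10.0% to 18.4%.
- For scale, 90% power with 95% intervals needs 320 evaluable per arm (319 gives 89.96%). With 20% non-evaluable that is 320/0.8 = 400 per arm, 800 in total.
- At ±1.5 the exact power with a 95% interval is 99.7%, so ±1.0 is the limit that binds.

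**Step 3: where the two readings disagree.** At SD 3.5 the half-width is 0.500 for the 90% interval and 0.596 for the 95% interval. The largest observed difference that passes ±1.0 is 1.0 − 0.500 = 0.500 in the first case and 1.0 − 0.596 = 0.404 in the second. Anything between these values passes one and fails the other. At a true difference of 1.0 the rejection rates are 5.0% and 2.5%.

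**Step 4: the full success rule.** The rule was taken as all four time points within ±1.5 and at least three of four within ±1.0. It was simulated with 300,000 draws (Monte Carlo standard error 0.0007), true difference 0, and one common between-time correlation. The documents do not give that correlation, so a range was used.

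| Assumed correlation | Power, 90% intervals | Power, 95% intervals | Passes only with 90% intervals |
|---|---|---|---|
| 0 | 94.5% | 83.7% | 10.8% |
| 0.3 | 93.3% | 82.9% | 10.3% |
| 0.5 | 91.7% | 81.9% | 9.7% |
| 0.7 | 90.1% | 80.5% | 9.6% |
| 0.9 | 89.0% | 79.8% | 9.3% |

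No simulated trial passed with the 95% intervals and failed with the 90% intervals. None of the correlations tried brings the 95% column back to 90%.

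**The case against.** The strongest reply is that the deciding level is already clear. Every analysis passage that gives a numerical level for the treatment-difference interval says 95%, and nothing plans a 90% interval. The synopsis and protocol 10.3 put the success rule straight after the 95% sentence. On this view the SAP's 100(1-2α)% is a textbook identity, which means α = 0.025 when read with the 95% interval in the same section. SAP section 10 declares no deviation from the protocol, and section 11 has the SAP final before database lock, so a move to 90% would be visible.

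Much of this stands as a reading of intent: 95% is the better-supported level. It does not remove the problem. The value 0.025 appears nowhere, the SAP's rule is worded as a necessary and sufficient condition, and the one α on paper contradicts 95%. If the 95% reading is accepted, the power statement in three places is wrong for the planned analysis.

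Other points are fair:
- The 90% is not a miscalculation. The fault is a mismatch between the sizing and analysis sections.
- The p-value sentence in protocol 10.3 sits in the change-from-baseline paragraph, so it bears on the secondary endpoint. For the primary endpoint, the p-value without a stated α is in SAP 9.6.1.
- The rule tolerates one of four time points outside ±1.0, so per-time-point power is not the power of the trial. Step 4 shows that the loss is about the same size under the full rule.
- If all 333 per arm were evaluable, per-time-point power with 95% intervals would be 91.5%. The plan itself assumes that 20% are not evaluable, and the primary analysis uses the per protocol population.

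**Conclusion.** The point holds. The stated 90% is correct for two one-sided tests at 0.05 each and does not describe the 95% intervals of the primary analysis. With those intervals, 266 evaluable per arm gives 81.6% per time point at ±1.0, about 8 points lower. For the full rule it gives 79.8% to 83.7%, against 89.0% to 94.5% with 90% intervals. These figures rest on the plan's SD of 3.5 and true difference of 0. The full-rule figures also rest on an assumed equal correlation of 0.9 to 0.

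SAP 9.6.1 and 9.6.2 leave α without a value, and no single α makes all the passages agree. For an identical product, the verdict would turn on the choice of interval in about 9% to 11% of trials. This should be fixed. The error lies on the side of lost power, not of false claims of equivalence, provided that the 95% interval is confirmed as the deciding one.

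**What to change.** 1. In protocol 10.3 and SAP 9.6.1 and 9.6.2, state α = 0.025 for each one-sided test. The 100(1-2α)% interval is then the 95% interval that the protocol already specifies, and the p-values and intervals give the same decision.
2. In the synopsis, protocol 10.5 and SAP 8.6, restate the power: with 266 evaluable per arm and two-sided 95% intervals, about 82% per time point at ±1.0. Add about 80% to 84% for the full four-time-point rule, with the correlation assumption of 0.9 to 0 stated beside it.
3. In the same three places, remove the 95% attached to the equivalence limits. The limits are fixed margins and carry no confidence level, and the label hides which level the sizing used.

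The cost is wording only, with no added enrolment. The published power becomes less favourable, and the more lenient 90% reading is closed off. The SAP change should be made before database lock and unblinding.

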8.7 Interim Analysis

There is no interim analysis planned for the study.

8.8 Statistical Software

All statistical analyses will be performed with SAS®, Version 9.4 or later.

9 Statistical Analyses

9.1 Subject Disposition

Subject disposition will be tabulated with number and percentages of patient's screened, screen failed, randomized, dosed, completed the study according to the protocol or discontinued the study prematurely. The patients who prematurely discontinued the study and the reasons for their discontinuation will be presented. The disposition table will be summarized using "Screened population" by treatment group.

9.2 Demographic Data and Baseline Characteristics

The demographic data and baseline characteristics will be summarized using descriptive statistics or by frequency and percentage for the applicable parameters using SAF Population by treatment group.

- Age
- Gender
- Race
- Ethnicity
- Iris color
- Childbearing potential
- Best Spectacle-Corrected Visual Acuity Score (Left / Right Eye)

[figure not shown]
9.3 Medical History

All general medical history conditions and concomitant diseases will be coded using MedDRA version 24.0. General medical history conditions and concomitant diseases will be summarized by system organ class, preferred term and by treatment group using SAF population. The version of the utilized dictionary will be presented as part of the provided tables and listings. Listing of medical history will be provided.

9.4 Prior and concomitant medication

Prior and concomitant medications will be assessed at screening, while concomitant medications will be assessed at each subsequent study visit. Medications will be coded using WHODG MAR 1, 2021.

Medication will be classified as prior, if the end date is known and is prior to the first use of the study medication. Medications that are ongoing or ended after the first use of the study medication will be classified as concomitant. If the end date of the medication is unknown, it will also be considered as concomitant. Handling of missing date explained in section (Imputation of missing data section 8.5).

Prior and concomitant medications will be separately summarized by ATC class (the highest available level), preferred name and treatment group for the safety population. Listings will be presented for prior and concomitant medications.

9.5 Protocol Deviation

Protocol deviations will be summarized by Number of patients with protocol deviations (Major/). Protocol deviations will also be summarized by Number of patients with Major/Minor Protocol Deviations by its category and treatment using SAF population.

Table and Listings will be presented for all the protocol deviations and separate table and listings.

9.6 Efficacy Analysis

Primary and secondary efficacy endpoint will be analysed using the PP population.

9.6.1 Primary Efficacy Endpoint

Mean difference in IOP of both eyes between the two treatment groups at four time points, i.e., at approximately 8:00 a m. (hour 0; before the morning drop) and 10:00 a.m. (2 hours) at the Day 14 (Week 2) and Day 42 (Week 6) visits

IOP measurements will be taken using a Goldmann applanation tonometer. IOP will be measured at least twice in each eye with the right eye measured first. If the difference of the first 2 measurements is ≤ 1 mm Hg, the average of these 2 measurements will be used as the IOP data for this eye. If the difference is > 1 mm Hg, a third measurement will be taken, and the median of these 3 measurements will be used as the IOP data for this eye.

Two-sample 95% CIs around the difference in the mean IOP (both eyes) at each timepoints i.e., at approximately 8:00 a m. [hour 0; before the morning drop] and 10:00 a.m. [hour 2] at the Day 14 [Week 2] and Day 42 [Week 6]) visits will be constructed using a two-sample t-distribution.

The hypotheses for a two-sample equivalence test are:

 H_o : $\mu < \Theta_L$ or $\mu > \Theta_U$

[figure not shown]
 $H_1: \Theta_L \le \mu \ge \Theta_U$

Where.

μ: Difference in mean IOP between treatment groups within study period

 $\Theta_{L:}$ -1.5mm Hg and (-1.0mm Hg)

 $\Theta_{U:}$ 1.5mm Hg and (1.0mm Hg)

The overall p-value of the equivalence test will be reported, which is the larger of the two p-values of the tests L and U. Rejection of H_0 in favour of H_1 at significance level α occurs if and only if the 100 (1-2 α) % confidence interval for μ is contained within (-1.5, 1.5) and (-1.0, 1.0). Two sample t-test also assumes equality of variances in the treatment groups, hence depending on the results from Levene's test, CI, and p-values from Equal (Pooled) or Unequal (Satterthwaite) variance will be reported.

This analysis also will be tested for ITT population to check the robustness of the result.

[figure not shown]

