### **6.3.2 Visit 2 (Day 0) Baseline/Randomization**

- Confirmation of subject eligibility and reassessment of inclusion/exclusion after washout
- Randomization
- Concomitant medications (systemic and ophthalmic)
- Adverse event assessment (reported, elicited, observed)
- Urine pregnancy test (if applicable)
- Heart rate and blood pressure
- BSCVA
- Slit lamp biomicroscopy
- Intraocular pressure 8:00 AM  $\pm$  30 min: by Goldmann applanation tonometer (this will be the qualifying IOP for enrollment)
- Dispensation of study medication and study medication compliance diary after IOP reading.
- Intraocular pressure at 10:00 AM  $\pm$  30 min: by Goldmann applanation tonometer
- Subjects will be instructed to use their assigned study medication at home starting the next day. Subjects will be instructed to shake the bottle well and then instill study medication into the inferior cul-de-sac of both eyes (OU) at 8.00 AM. ( $\pm$ 60 minutes), 4.00 PM. ( $\pm$ 60 minutes) and 10.00 PM. ( $\pm$ 60 minutes).
- Schedule next visit - subjects will be instructed to come for the next visit without instilling the morning dose on the visit date

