## **8.0 ASSESSMENT OF EFFICACY**

As per the OGD guidance, primary efficacy endpoint is the mean difference in IOP of both eyes between the 2 treatment groups at 4 time points, i.e., at approximately 8:00 a.m. (hour 0; before the morning drop) and 10:00 a.m. (hour 2) at the Day 14 (Week 2) and Day 42 (Week 6) visits

This will be done by measuring IOP at 08:00 AM  $\pm$  30 min and at 10:00 AM  $\pm$  30 min using Goldmann applanation tonometer at the baseline visit (Visit 2) and at the Day 14 (Week 2) and Day 42 (Week 6) visits.

The secondary efficacy endpoint is change from baseline in IOP of both eyes between the 2 treatment groups at 4 time points, i.e., at approximately 8:00 AM (hour 0; before the morning drop) and 10:00 AM (hour 2) at the Day 14 (Week 2) and Day 42 (Week 6) visits.

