In addition to these individual confidence intervals, a mixed effects repeated measures model, with random effect for subject, covariate for baseline IOP, and fixed effects for treatment and day/time (within subject repeated measures) will be fitted to the data. Appropriate covariance structure will be used to model the within subject, between time point variances. Individual and simultaneous confidence intervals will then be constructed based on this MMRM model at each of the time points. The 95% simultaneous confidence intervals will use the Tukey-Kramer method to adjust for multiple comparisons across all 4 time points.

The analyses of the efficacy variable will be completed on observed data only (without imputation). To check robustness of results, sensitivity analyses of the primary efficacy data will include using: a multiple imputation technique to impute missing data.

For the multiple imputation approach, the multiple imputation technique proposed by Rubin (1987) replaces each missing value with a set of plausible values and these imputed data sets are then analyzed by using standard procedures for complete data and combining the results from these analyses. A Markov chain Monte Carlo (MCMC) method, which can be implemented within SAS software that assumes multivariate normality, will be used for imputation.

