## **11.7 Amendments to the Protocol**

All changes or deviations of the trial must be confirmed in writing. The amendments to protocol will be made jointly between the CRO (if applicable), the Sponsor and Investigator(s). Protocol amendment(s) will be signed off in the same way as the protocol.

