9.6.2 Secondary Efficacy Endpoints

Change from baseline in IOP of both eyes between the 2 treatment groups at 4 time points, i.e., at approximately 8:00 AM. (hour 0; before the morning drop) and 10:00 AM. (hour 2) at the Day 14 (Week 2) and Day 42 (Week 6) visits.

For change from baseline IOP, baseline will refer to the time-matched measure at Visit 2. Change from baseline will be calculated as visit x – baseline. The overall p-value of the equivalence test will be reported, which is the larger of the two p-values of the tests L and U. Rejection of H0 in favour of H1 at significance level α occurs if and only if the 100 (1-2 α) % confidence interval for μ is contained within (-1.5, 1.5) and (-1.0, 1.0). Two sample t-test also assumes equality of variances in the treatment groups, hence depending on the results from Levene's test, CI and p-values from Equal (Pooled) or Unequal (Satterthwaite) variance will be reported. This mean IOP must be within \pm 1.5 mm Hg using the PP population for all time points measured and within \pm 1.0 mm Hg using the PP population for the majority of time points measured.

This analysis also will be tested for ITT population to check the robustness of the result.

In addition to these individual confidence intervals, a mixed effects repeated measures model, with random effect for subject, covariate for baseline IOP, and fixed effects for treatment and day/time (within subject repeated measures) will be fitted to the data. Appropriate covariance structure will be used to model the within subject, between time point variances with order of treatment Visit treatment*visit and baseline as covariate. Individual and simultaneous confidence intervals will then be constructed based on this MMRM model at each of the time points. The 95% simultaneous confidence intervals will use the Tukey-Kramer method to adjust for multiple comparisons across all 4 time points. Above mentioned analysis will be performed on PP and ITT population.

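### The primary equivalence CIs ignore baseline IOP, although it is collected and a baseline-adjusted model is already planned as secondary; adjusting would narrow the deciding intervals without extra patients

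*SAP*

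**What the plan says.** **Deciding analysis.** SAP 9.6.1 states that the 95% CIs for the difference in mean IOP of both eyes at the Day 14 and Day 42 "visits will be constructed using a two-sample t-distribution". Levene's test selects pooled or Satterthwaite variance, and there is no covariate. Protocol 10.3 asks for two-sided 95% CIs at the four time points in the per-protocol (PP) set. All four must lie within ±1.5 mm Hg and the majority within ±1.0 mm Hg.

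**Baseline data.** Protocol 8.0 schedules IOP at 8:00 and 10:00 "at the baseline visit (Visit 2) and at the Day 14 (Week 2) and Day 42 (Week 6) visits". Protocol 6.3.2 says of the 8:00 reading at Visit 2 that "this will be the qualifying IOP for enrollment". It adds: "Subjects will be instructed to use their assigned study medication at home starting the next day". Both Visit 2 readings are therefore pre-treatment.

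**Adjusted analysis already planned.** Protocol 10.3 adds a repeated-measures model "with random effect for subject, covariate for baseline IOP, and fixed effects for treatment and day/time". SAP 9.6.2, headed Secondary Efficacy Endpoints, repeats it and says: "Individual and simultaneous confidence intervals will then be constructed based on this MMRM model at each of the time points". It closes with: "Above mentioned analysis will be performed on PP and ITT population". The same SAP section plans an equivalence test on time-matched change from baseline. In the protocol the model stands in the general efficacy section as an addition to the individual CIs. Neither document lets it decide equivalence.

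**The concern.** An equivalence claim turns on CI width. Baseline IOP is usually among the better predictors of on-treatment IOP, and here it is measured at matching clock times before any dose. A linear adjustment for it estimates the same difference in mean IOP with a smaller standard error. Leaving it out of the deciding interval gives up precision that the trial already pays for.

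The practical risk is a narrow miss. If the t interval crosses a limit at a time point where the adjusted interval does not, the plan lets the less precise result stand, and the adjusted result can only be reported beside it. Recruitment cannot make up the loss, because Protocol 6.5.3 does not replace dropouts and SAP 8.2 removes 20 subjects from one site from the efficacy analysis.

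**Working it through.** **Inputs from the documents.** 266 evaluable per arm, SD 3.5, true difference 0, limits ±1.0, α 0.05, stated power 90%, 20% non-evaluable (Protocol 10.5, SAP 8.6); 95% CIs and the ±1.5/±1.0 rule (Protocol 10.3).

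**Assumptions.** 3.5 is the SD of a subject's mean raw IOP, equal in both arms. The baseline-to-follow-up correlation r is not given, so a range is shown.

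**1. The plan's own figure.** n = 2 × [SD × (z(1−α) + z(1−β/2)) / margin]² = 2 × [3.5 × (1.645 + 1.645) / 1.0]² = 265.1, so 266 per arm; 266 / 0.8 = 332.5, so 333. An exact t-based calculation gives 90.0% power. The figure reproduces only with 0.05 per one-sided test, which corresponds to a 90% CI. With the 95% CI that decides, the same formula with 1.960 for the first z gives 319 per arm, and power at 266 is 81.6%.

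**2. Effect of adjustment at one time point.**
- Adjusted SD = 3.5 × √(1 − r²).
- CI half-width = t(0.975) × SD × √(2/266).
- Power at difference 0 is the average of 2Φ((1.0 − t × estimated SE) / SE) − 1 over the sampling distribution of the variance, with 530 df unadjusted and 529 adjusted.
- Equivalent unadjusted n = 266 / (1 − r²).

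| r | SD | 95% half-width (mm Hg) | Power, 95% CI, diff 0 | Power, 95% CI, diff 0.2 | Power, 90% CI, diff 0 | Equivalent n per arm |
|---|---|---|---|---|---|---|
| unadjusted | 3.50 | 0.596 | 81.6% | 72.6% | 90.0% | 266 |
| 0.2 | 3.43 | 0.584 | 83.8% | 74.7% | 91.3% | 277 |
| 0.3 | 3.34 | 0.569 | 86.3% | 77.3% | 92.9% | 292 |
| 0.4 | 3.21 | 0.546 | 89.7% | 80.9% | 94.8% | 317 |
| 0.5 | 3.03 | 0.516 | 93.4% | 85.5% | 96.9% | 355 |
| 0.6 | 2.80 | 0.477 | 96.9% | 90.7% | 98.6% | 416 |

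At r of about 0.41 the 95% CI analysis regains 90% power. If r is zero, the cost is one degree of freedom in 530, and power stays at 81.6%.

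**3. Full decision rule.** Simulation of four correlated differences, all within ±1.5 and at least three within ±1.0, 95% CIs, true difference 0. With an assumed correlation of 0.7 between follow-up time points, power is about 80.6% unadjusted and 86%, 90% and 94% at r = 0.3, 0.4 and 0.5. Varying that correlation from 0.5 to 0.8 gives 80–82% unadjusted and 86–88%, 89–92% and 94–96% adjusted.

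**4. Does the change-from-baseline test do the same job?** Its variance is SDf² + SDb² − 2r × SDf × SDb, where f is follow-up and b is baseline. It beats raw IOP only if r exceeds SDb / (2 × SDf). With equal SDs of 3.5 the break-even is r = 0.5, and power is 58.8%, 70.3%, 81.6% and 91.4% at r = 0.3, 0.4, 0.5 and 0.6. If eligibility reduced the baseline SD to 2.5 (assumed), break-even is 2.5/7 = 0.36, and power at r = 0.3 and 0.4 is 77.1% and 84.9%. In both cases ANCOVA does better at those values of r (86.3% and 89.7%).

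**The case against.** The strongest reply is that nothing here is an error. Under randomisation the two-sample t interval is valid for the stated endpoint, adjusted CIs are already prespecified on PP and ITT, and only the sponsor's chance of success is affected. That is correct, and it is why this is a recommendation rather than a defect that must be repaired.

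Other points stand in part:

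- **The gain is uncertain.** The qualifying role of the 8:00 baseline reading may restrict its range and lower r. At r = 0.1 power rises only from 81.6% to 82.2%. The downside of adjusting, however, is negligible.
- **The low starting point has another cause.** The 81.6% reflects sizing at one-sided 0.05 against a 95% CI. On the sizing basis unadjusted power is already 90.0%, and r = 0.3 adds about 3 points. The gain shrinks but does not vanish.
- **Regulatory acceptance cannot be checked here.** The documents tie the endpoint to agency guidance (Protocol 3.3.4 and 8.0). Protocol 10.3 asks for CIs of the treatment difference in mean IOP, which a linear adjustment still estimates, but whether the agency accepts an adjusted primary CI must be confirmed.
- **Timing needs care.** The SAP is dated 20 Sep 2023 and already excludes a site from efficacy. A late change of primary estimator must be shown to be made blind.
- **Baseline imbalance is not a separate bias.** One standard error of imbalance is 3.5 × √(2/266) = 0.30 mm Hg if baseline SD is 3.5, which moves the raw difference by about 0.15 at r = 0.5. Chance imbalance of this kind is already in the unadjusted standard error. Adjustment removes that part of the variability; it does not correct an invalid test.

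**Conclusion.** The point holds. The deciding CIs are unadjusted, the covariate is collected before treatment, and the adjusted model is planned without decision status. For r between 0.3 and 0.5, adjustment narrows the 95% half-width from 0.596 to between 0.569 and 0.516 mm Hg. That is worth 26 to 89 more evaluable subjects per arm (292 − 266 to 355 − 266). Full-rule power rises from about 81% to between 86% and 94%, at a true difference of 0 and a correlation of 0.7 between time points.

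These figures rest on 3.5 being the raw-IOP SD and on an r that the documents do not give. If 3.5 were instead a baseline-adjusted SD, the raw SD at r = 0.5 would be 3.5 / √0.75 = 4.04, and unadjusted power would be about 63%. The direction of the result does not depend on these assumptions; its size does. The change should be made, but it is not essential to validity.

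**What to change.** Before unblinding, amend SAP 9.6.1, and Protocol 10.3 to match, in one of two ways:

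- **ANCOVA at each time point.** Outcome: the subject's mean IOP of both eyes. Terms: treatment and time-matched Visit 2 IOP.
- **Promote the SAP 9.6.2 mixed model.** State that its time factor covers all four day/time points, use time-matched baseline, and include treatment-by-time and baseline-by-time terms. Let the individual 95% CIs decide, not the simultaneous ones, since the rule is applied time point by time point.

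Apply the existing ±1.5 and ±1.0 rule to the adjusted difference, and keep the two-sample t CI as a named sensitivity analysis. Confirm regulatory acceptance first, and record that the change was made without access to treatment codes. If unblinding has already happened, leave the t CI primary and report the adjusted CI beside it.

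The cost is a wording change in two places plus amendment approval; Protocol 11.7 states: "Protocol amendment(s) will be signed off in the same way as the protocol". No new data, visits or patients are needed.
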